**Study protocol**

**Objectives**

The aim of the study is to investigate the effectiveness of the hand exercise program and demonstrate its influence on hand function, quality of life, as well as anxiety and depression in patients with systemic sclerosis.

**Material and Methods**

**Study design and study population**

The current study was designed as a single-blind, prospective, randomized controlled, comparative study with a 2-month follow-up period, conducted in a rheumatology outpatient clinic of a university hospital, between July 2016-June 2019. Female patients with SSc who fulfilled the 2013 ACR/EULAR classification criteria for systemic sclerosis were included in the study. Patients with neurological disorders, arthritis, myositis, amputation of fingers, serious contracture resisting hand grip and history of undergoing hand surgery were excluded from the study. The study protocol was approved by the local ethics committee of Cukurova University (Approval date: 15-July-2016, number: 55). Written informed consent form was obtained from all patients according to the Helsinki declaration.

**Evaluation of Patients**

The demographic variables and socio-economic status of patients were recorded at the beginning of the study. The time from the beginning of non-Raynaud's phenomenon symptoms was regarded as disease duration. The systemic sclerosis subsets including limited systemic sclerosis and diffuse systemic sclerosis were classified according to the definition of LeRoy et al. The organ involvements including interstitial lung disease, pulmonary arterial hypertension, scleroderma renal crisis, and gastroesophageal reflux disease were recorded based on the medical data. The present or absent of clinical variables such as Raynaud's phenomenon, digital pitting scars, arthralgia, sclerodactyly, calcinosis, color change, and telangiectasias was noted as well. Patients were questioned about cigarette smoking (package/years), medical drug information (previous and current) and comorbidities causing hand dysfunction (diabetes mellitus, atherosclerosis, thyroid diseases). Additionally, the laboratory results including anti-nuclear antibody, anti-Scl 70 antibody, anti-centromer antibody, complement levels (C3 and C4), erythrocyte sedimentation rate (ESR) (mm/h), and C-reactive protein (CRP) (mg/dl) were recorded.

The evaluation of disease activity and severity was performed by Valentini disease activity index and Medsger disease severity scale. Modified Rodnan Skin Score was used to assess the severity and the extent of

skin involvement. Hand involvement of patients was exhaustively evaluated by means of physical examination and indexes assessing the hand function. The finger range of motion was performed by the measure of finger-to-palm. The functional disability of hand was examined by Hand mobility in Scleroderma (HAMIS) test. Hand function was also evaluated by Duruoz Hand Index (DHI). Handgrip strength was measured by hydraulic hand dynamometer (JAMAR®, USA) according to the standard protocol. The physical function and quality of life were assessed by using Health Assessment Questionnaire-Disability Index (HAQ-DI) and Short-Form 36 (SF-36). Psychological status was evaluated by using Beck Depression Inventory (BDI) and Beck Anxiety Inventory (BAI).

### **Randomization**

The computerized block randomization method was used to randomize subjects into groups. Each block contained 10 subjects consisting of 5-intervention and 5-control subjects. We simulated seven blocks with a total of 70 subjects at the beginning of the study. The 6th block was designed to compensate for the study population in terms of loss to follow-up. The 7th block that was designed to use if needed was planned for compensation of the patients who would be excluded from the analysis. Randomization was managed by a physiatrist who trained patients according to which group they were in. The second physician who was blinded evaluated patients.

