### **Intervention**

The patients were randomized into an exercise (n=25) and a control (n=25) group. Both groups were informed about systemic sclerosis and they received the printed materials that include recommendations such as avoiding cold and trauma. The treatment group participated in a single hand exercise training (isometric hand exercise and self-administered stretching) applied by a physiatrist. Isometric exercise was told as the ball squeeze exercise. Accordingly, patients squeezed the soft small ball for 60 seconds. This repeated 15 times in each set. Three sets were recommended per day. The stretching exercises were as follows; i) forearm supination and pronation, ii) wrist flexion and extension, iii) finger flexion, extension and abduction iv) thumb flexion, extension and abduction. Holding each stretch was recommended for 30 seconds. Thereafter, patients took instructions illustrating the exercises. The 8-week intervention consisted of isometric hand exercise 15-times/3

set and self-administered stretching repeated 10-times/2 set per day. Compliance was assessed by a checklist, which included all information on how to exercise and how many times to do them.

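### The physiatrist who trains patients by arm also manages randomization in fixed 5+5 blocks, with no concealment described, so upcoming allocations may be known or partly predictable

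*Combined protocol and SAP*

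**What the plan says.** Three statements in the Randomization section matter here.

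- Roles: "Randomization was managed by a physiatrist who trained patients according to which group they were in".
- Block structure: "Each block contained 10 subjects consisting of 5-intervention and 5-control subjects".
- List: "We simulated seven blocks with a total of 70 subjects at the beginning of the study".

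The Intervention section agrees on the trainer's role: the exercise session was "applied by a physiatrist". The Study design and study population section places the trial in one clinic, and no stratification is described, so there is a single allocation sequence. It calls the trial single-blind. The one separation of roles that is described concerns assessment: "The second physician who was blinded evaluated patients".

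The protocol does not mention envelopes, central or third-party allocation, or a rule that assignment follows consent and baseline assessment. It does not say who produced the list, who could see it, who screened and enrolled patients, or whether the block size was withheld from recruiting staff.

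**The concern.** Randomization protects the comparison only if whoever decides that a patient enters, and when, cannot foresee the arm. Here the manager of the allocation is necessarily unblinded to past assignments, and every block has the same length and split. If that person also influences entry, patients thought more likely to benefit could be entered when an exercise slot is expected, and others delayed.

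Blinded evaluation does not address this. It limits bias in measuring outcomes, not in who is enrolled. The analysis does not repair it either. The Statistical analysis section compares changes from baseline between arms by Mann-Whitney U test, without adjustment for baseline characteristics. Motivation for home exercise, a plausible basis for steering, is not among the baseline variables listed under Evaluation of Patients. Any selection effect would be mixed with the exercise effect on grip strength, the primary outcome.

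**Working it through.** **Inputs.** Block of 10 split 5:5, and seven blocks (Randomization); 25 + 25 patients randomized (Intervention); target difference 4 kg (Sample size).

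**The plan's own figures.** 7 × 10 = 70, as stated. Five full blocks give 5 × 10 = 50 = 25 + 25, which matches the Intervention section.

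**Case A: the list is visible to the manager.** All 10 of 10 upcoming allocations are known.

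**Case B: only past assignments and the block size are known.**

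*Allocations that are certain.* Once one arm's five places are used, the rest of the block is determined. The expected number of exercise places after the last control place is 5/6, and the same holds with the arms reversed. The total is 10/6 = 1.67 per block of 10 (16.7%), or 5 × 1.67 = 8.3 of 50. The last place in each block is always certain.

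*Allocations guessed correctly.* The best strategy is to guess the arm with more places left, with ties guessed at 1/2. With a and c places left, the expected number correct is

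G(a,c) = max(a,c)/(a+c) + [a/(a+c)]·G(a−1,c) + [c/(a+c)]·G(a,c−1), with G(0,0) = 0.

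For 5+5 this equals 5 + 2⁹/C(10,5) − 0.5 = 5 + 512/252 − 0.5 = 6.53 of 10 (65.3%). Over 50 patients that is 32.7 correct, against 25 by chance.

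**Would other block sizes help?** The same calculation gives these guess rates for fixed blocks:

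| Block size | Correct guesses |
|---|---|
| 4 | 70.8% |
| 6 | 68.3% |
| 8 | 66.6% |
| 10 | 65.3% |

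Smaller blocks are easier to guess. An undisclosed mix of 8, 10 and 12 gives (5.33 + 6.53 + 7.72)/30 = 19.58/30 = 65.3%, the same as fixed blocks of 10, because guessing the arm that is behind needs no knowledge of block size. Mixing removes certainty at block ends and little else. If the recruiter knows neither the list nor past assignments, the rate is 50%.

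**Illustration in kg (assumed, not from the documents).** Suppose steering raises a patient's expected grip change by η when exercise is predicted and lowers it by η when control is predicted. With a proportion p predicted correctly, the exercise arm shifts by η(2p − 1) and the control arm by −η(2p − 1). The between-arm bias is 2η(2p − 1).

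- p = 0.653: 2η × 0.306 = 0.61η, or 0.6 to 1.2 kg for η of 1 to 2 kg.
- p = 1: 2η, or 2 to 4 kg for the same η. This is a ceiling that requires all 50 patients to be steered.
- p = 0.5: no bias.

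**The case against.** The strongest reply is that most of this rests on silence. Managing randomization need not mean holding an open list, and the protocol does not say that the physiatrist decided who entered or when. Selection bias needs both foresight and control of entry in the same hands, or communication between them. In a rheumatology clinic, enrolment by someone other than the physiatrist fits the text equally well. That stands, and it limits the conclusion to a risk.

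A reader might infer that allocation was in fact unconcealed. The documents do not support this: they describe a combination of roles and no safeguard, but not who could see the list. A reader might also set the 2 to 4 kg ceiling beside the 4 kg target and infer that selection could produce the whole planned effect. That is not supported either. No document supports the assumed 1 to 2 kg steering effect. The ceiling also needs every patient to be steered, and steered on future change rather than baseline level, because the analysis compares changes.

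The reply does not remove the point. The dual role and the fixed blocks are stated, and past assignments are known to the manager whether or not the list is open. The predictability figures follow from the block structure once past assignments and block size are known.

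**Conclusion.** The concern holds as a risk that the plan does not exclude. The main weakness is the combined role without described concealment; the fixed block of 10 is secondary. Upcoming allocations are fully known if the manager sees the list. Otherwise 1.67 of 10 are certain and 6.53 of 10 guessable, on the assumption that past assignments and block size are known to whoever influences entry. No bias is demonstrated and its size in kg cannot be derived from the documents. The point deserves action because blinded assessment and the planned analysis would not correct such a bias, while the remedy is cheap.

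**What to change.** - Have an existing staff member other than the training physiatrist hold the list and prepare sequentially numbered, opaque, sealed envelopes.
- Have the blinded second physician, not the trainer, confirm eligibility and record a dated baseline assessment after consent. Open the next envelope only then. Envelopes alone hide the list but not the trainer's knowledge of past assignments, so keeping the trainer out of eligibility and timing decisions is essential.
- Do not disclose the block size to recruiting staff.
- Varying the block size is optional. It would require a new list and a redefinition of the sixth and seventh blocks, which the plan reserves for losses and exclusions, and it leaves the guess rate at about 65%.

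The cost is protocol wording, a set of envelopes and minor logistics, with no extra staff or patients.

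If enrolment is already complete (the protocol gives July 2016 to June 2019), state who generated and held the list, who enrolled patients and how assignments were concealed, or report the lack of concealment as a limitation on the conclusion.

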### **Sample size**

Handgrip strength was determined as the primary outcome measure. According to the literature, handgrip strength has been reported to have a standard deviation between 6 and 7 [35]. Accordingly, standard deviation as 7 and autocorrelation coefficient as 0.3 were accepted in the current study evaluating the average of three consecutive measurements of handgrip strength. The sample size was calculated as 24 participants for each group in order to detect at least 4 kg differences with a 95% confidence interval and 80% power.

DHI was defined as the secondary outcome measure. We calculated the mean standard deviation as the mean of the total DHI for two time-points and two groups  $(20.20+16.22+17.1+17.85)/4=17.5$  [23]. We expected at least 5-6 points regression in the control group and at least >5-6 points improvement in the treatment group, so that, we assumed that there could be at least 12 points differences between groups. The number of observations, to find this difference significant at alpha=0.05 with 80% power, was calculated to be at least 23 per group.

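### The stated components of the DHI difference add to a minimum of about 10 points, not 12, so the 80% power claim does not follow; about half of the contrast is control worsening given without a reason

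*Combined protocol and SAP*

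**What the plan says.** The Sample size section names handgrip strength as primary (24 per group) and DHI as secondary. For DHI it gives an expected change in each arm: "We expected at least 5-6 points regression in the control group and at least >5-6 points improvement in the treatment group". From these it concludes that "we assumed that there could be at least 12 points differences between groups". The number needed "to find this difference significant at alpha=0.05 with 80% power" is put at 23 or more per group.

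The standard deviation is an average of four published values ("20.20+16.22+17.1+17.85)/4=17.5"). The citation in that paragraph is attached to these values. The expected control worsening carries no citation and no explanation.

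Elsewhere, the study design section gives a 2-month follow-up, and the Intervention section gives 25 patients per group. Under Statistical analysis, changes from baseline are compared by Mann-Whitney U test and judged at p below 0.05. No between-group estimate with a confidence interval is mentioned.

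**The concern.** There are two linked problems. First, the sum does not give what is claimed. If each arm moves by at least 5–6 points in opposite directions, the guaranteed separation is just over 10. Calling 12 the minimum takes the upper end of both ranges and labels it a floor.

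Second, about half of the contrast is not treatment benefit at all. It is decline in the control arm within 8 weeks, and the reader is not told why that is expected. The power claim depends heavily on it.

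Hand function is a named objective, and DHI has its own 80% power statement. If that statement is too optimistic, a non-significant DHI result is more likely than readers will suppose. With only a p-value to go on, it could be taken as evidence that exercise does not help hand function.

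**Working it through.** **Inputs (Sample size and Intervention sections).** Control worsening 5–6 points; treated gain above 5–6 points; contrast used 12; SD 17.5; alpha 0.05; power 80%; 23 per group required; 25 per group randomized. Sidedness is not stated for DHI. Two-sided is assumed, in line with the handgrip wording ("with a 95% confidence interval and 80% power").

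**1. The contrast.** Lower ends: 5 + 5 = 10. Upper ends: 6 + 6 = 12. The range is 10–12, and the floor is about 10.

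**2. The plan's figure of 23.** The usual formula is n = 2(1.960 + 0.842)² × SD² / Δ² = 15.70 × SD² / Δ².
- SD 17.5, Δ 12: 15.70 × 306.25 / 144 = 33.4, so 34 per group. This is not 23.
- Multiplying by (1 + 0.3)/2 = 0.65, the variance factor for averaging two time-points with the correlation of 0.3 stated for handgrip: 21.7, so 22 per group.
- The four printed SDs actually average 71.37/4 = 17.84. With that value and the same factor: 22.6, so 23 per group.

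So 23 is reproducible, but only with an input that the DHI paragraph does not state. The steps below take the plan's calibration as given, so that the effect of the contrast is seen on its own.

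**3. Calibration.** For a two-sided two-sample t-test (noncentral t), 23 per group gives 80% power at a standardized difference d = 0.845. Setting this equal to 12 points, a contrast of Δ points has d = 0.845 × Δ/12 and noncentrality d × √(n/2).

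**4. Power by contrast.**

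| Scenario | Δ (points) | d | Power, 23 per group | Power, 25 per group |
|---|---|---|---|---|
| Top of both ranges (as used) | 12 | 0.845 | 80% | 83% |
| Bottom of both ranges | 10 | 0.704 | 65% | 68% |
| Half the control worsening, upper (3 + 6) | 9 | 0.634 | 56% | 59% |
| Half the control worsening, lower (2.5 + 5) | 7.5 | 0.528 | 42% | 45% |
| Stable controls, gain of 6 | 6 | 0.422 | 29% | 31% |
| Stable controls, gain of 5 | 5 | 0.352 | 21% | 23% |

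**5. Sensitivity to the calibration.** With SD 17.5 in a plain two-sample t-test at 25 per group, power is 66% for 12 points, 51% for 10, 22% for 6 and 17% for 5. The levels are lower throughout, and the pattern is the same.

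**The case against.** The best defence is that this is a loosely worded assumption for a secondary outcome. Handgrip needs the larger number (24 against 23), so nothing about the trial's size changes. That stands, and it limits the weight of the point.

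A reader might go further and infer that the documents contradict the control worsening. They do not:
- **Population.** The exclusions ("Patients with neurological disorders, arthritis, myositis, amputation of fingers, serious contracture resisting hand grip and history of undergoing hand surgery were excluded") do not select stable patients. No limit is set on disease duration or activity, so progressive disease is as eligible as stable disease. Advice to both groups ("Both groups were informed about systemic sclerosis and they received the printed materials that include recommendations such as avoiding cold and trauma") does not rule out decline. The documents are silent on the natural course of DHI.
- **The SD.** It is tempting to annualize 5–6 points per 8 weeks and set the result against 17.5. That SD is described by "We calculated the mean standard deviation as the mean of the total DHI for two time-points and two groups": it measures spread between patients at a time-point and says nothing about mean drift. The plan does not assume a constant rate over a year either.
- **Stable controls.** Zero control change is no better sourced than the assumption it would replace. It also treats the expected gain, which the plan states as a floor, as the exact gain. The cited two-group source may have informed the expected control change; that cannot be checked here.

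The power figures also rest on a t-test and on the plan's unexplained calibration, whereas the planned test is Mann-Whitney on change scores, whose SD is not given. They are indicative. None of this repairs the sum: the stated minimums still add to about 10.

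**Conclusion.** The point holds as an internal inconsistency plus an undisclosed dependence. The plan's own components support a contrast of 10–12 points, and at 25 per group that means power of about 68–83%, not a secure 80% for a minimum of 12. This needs no outside assumption about controls, only the plan's calibration, a two-sided 0.05 level and a t-test approximation.

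The lower figures are conditional. Power is 45–59% if controls worsen half as much as assumed, and 23–31% if they do not change and the treated gain is 5–6 points. In that last case a non-significant DHI result would be expected about 69–77% of the time even though exercise delivered the 5–6 point gain. These figures show how much rests on the unexplained worsening. They do not show that the worsening is wrong. The primary sample size is unaffected.

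**What to change.** In the Sample size section:
- State the DHI contrast as 10–12 points, and the power as about 68–83% at 25 per group, in place of 80% for a 12-point minimum.
- Give the source or reason for the expected control worsening, or say that there is none.
- Add one sensitivity sentence: with stable controls and a treated gain of 5–6 points, power is about 23–31%. Label it as an assumption. Do not substitute it for the planning assumption, since the section should still describe the calculation that was done.

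In the Statistical analysis section, add that the between-group difference in DHI change will be reported with a 95% confidence interval, and that a non-significant result will not be read as absence of effect.

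The cost is a few sentences and one extra reported interval. No patients or visits are added and handgrip stays primary. The downside is a less favourable stated power for DHI.

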### **Statistical analysis**

Statistical analysis was performed by IBM SPSS version 20.0 (SPSS Inc., Chicago, IL, USA). Descriptive statistics was used to analyze the demographic and clinical variables. The normality of the variables was checked by Shapiro-Wilk test. Non-parametric values were given as median and interquartile range. Between-group comparisons of continuous and categorical variables were performed by Mann-Whitney *U* test and Chi-square test, respectively. Within-group comparisons over time analyzed by Friedman test. Delta ( $\Delta$ ) values were calculated as the difference from baseline measurement to the second visit measurement.  $\Delta$  values were compared between groups by Mann-Whitney *U* test. In addition, apart from  $\Delta$  values, the percentages of improvement or worsening on grip strength, DHI, HAMIS, HAQ-DI, Beck Depression and Beck Anxiety were calculated according to the formula as  $[(\text{Last assessment} - \text{Baseline assessment}) / \text{Baseline assessment}] \times 100$ . Multiple Linear regression analysis was used to define the predictors impacting on the percentages of improvement or worsening of HAMIS, DHI, handgrip strength, and HAQ-DI. The results were considered as statistically significant when *p* values below 0.05.

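### The DHI sample size of 23 per group does not follow from the stated DHI inputs; power for the planned change comparison depends on a correlation the plan does not give, and the printed mean SD is wrong.

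*Combined protocol and SAP*

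**What the plan says.** The Sample size section names handgrip strength as the primary outcome (24 per group) and then adds a separate calculation for DHI: "DHI was defined as the secondary outcome measure." Its DHI inputs are:

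- **SD:** the mean of four SDs from a cited study, printed as "20.20+16.22+17.1+17.85)/4=17.5".
- **Difference:** opposite movements of about 6 points in the two groups, so that "we assumed that there could be at least 12 points differences between groups".
- **Error rates:** the sample size is set "to find this difference significant at alpha=0.05 with 80% power". Sidedness is not stated.
- **Result:** "The number of observations, to find this difference significant at alpha=0.05 with 80% power, was calculated to be at least 23 per group."

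No formula and no correlation are given for DHI. The only correlation in the plan belongs to the handgrip paragraph: "autocorrelation coefficient as 0.3 were accepted in the current study evaluating the average of three consecutive measurements of handgrip strength". The Statistical analysis section defines delta as the change from baseline to the second visit and says that these "values were compared between groups by Mann-Whitney" *U* test. The Intervention section gives 25 patients randomized to each group.

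**The concern.** The stated difference, SD, alpha and power fix the size of a simple two-group comparison, and 23 is about a third below it. Something else must have entered the calculation, and the plan does not say what. The 12 points are a difference between two changes, and the planned test is on changes, so the baseline to follow-up correlation is the natural missing input. Without it, the claimed 80% power for the named secondary outcome can be neither confirmed nor rejected. If the true power is well below 80%, a non-significant DHI result could be misread as evidence of no effect.

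**Working it through.** **Inputs.** From the Sample size section: difference 12, SDs 20.20, 16.22, 17.1 and 17.85, alpha 0.05, power 80%. From the Intervention section: 25 per group. Two-sided testing is assumed because the plan does not say.

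**1. Mean SD.** 20.20 + 16.22 + 17.1 + 17.85 = 71.37, and 71.37/4 = 17.84. The printed 17.5 would need a sum of 70.0.

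**2. Plain two-group comparison.** n per group = 2(1.96 + 0.8416)² SD²/12², with (1.96 + 0.8416)² = 7.849.

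| SD | n, normal | n, t-based | Power at 23, normal / t |
|---|---|---|---|
| 17.5 | 33.4, so 34 | 35 | 64.3% / 62.3% |
| 17.84 | 34.7, so 35 | 36 | 62.6% / 60.7% |

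The SD slip alone moves n by one and power by about 1.5 points. One-sided testing would still need 27 to 29.

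**3. A route that does reach 23.** Take the handgrip value of 0.3 as the DHI correlation and analyse the mean of baseline and follow-up. The variance factor is (1 + 0.3)/2 = 0.65.

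- SD 17.84: 0.65 × 34.7 = 22.6, so 23 (normal); 23.6, so 24 (t-based).
- SD 17.5: 0.65 × 33.4 = 21.7, so 22 (normal); 22.7, so 23 (t-based).

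The same kind of formula reproduces the handgrip figure. For three measurements with correlation 0.3 decaying by lag, the variance factor is [3 + 2(0.3 + 0.3 + 0.09)]/9 = 0.487, and n = 2 × 7.849 × 49 × 0.487/16 = 23.4, so 24. This may therefore be where 23 came from, but that is inference.

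**4. The comparison actually planned.** The SD of change is SD × √[2(1 − r)], where r is the baseline to follow-up correlation. With SD 17.84 and a true difference of 12 points:

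| Assumed r | SD of change | Power at 23, t | Power at 25, t | Power at 23, Mann-Whitney | Power at 25, Mann-Whitney |
|---|---|---|---|---|---|
| 0.3 | 21.11 | 47% | 50% | 45% | 48% |
| 0.5 | 17.84 | 61% | 64% | 58% | 62% |
| 0.7 | 13.82 | 82% | 85% | 79% | 83% |

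The Mann-Whitney figures are simulated (20,000 runs, normally distributed changes).

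- At r = 0.3 the change comparison needs 49 (normal) or 50 (t-based) per group.
- 80% power at 23 needs r of 0.656 to 0.671 (SD 17.5) or 0.669 to 0.683 (SD 17.84); each range runs from the normal to the t-based value.
- 80% power at 25 with SD 17.84 needs r of 0.640 to 0.654, or about 0.68 for Mann-Whitney.
- At 25 per group and r = 0.5, the difference detectable with 80% power is about 14.4 points.

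**The case against.** The strongest reply is that a coherent method may lie behind both sample sizes. Averaging repeated measurements with correlation 0.3 gives 24 for handgrip and, with the printed SD of 17.5 and a t-based calculation, 23 for DHI. On that view the fault is poor reporting, not wrong arithmetic. This stands in part: it would be wrong to say that no formula gives 23. It does not rescue the power claim. Neither the 0.3 nor the averaging is stated for DHI, and the average of baseline and follow-up is not what the Statistical analysis section tests. Averaging in a baseline that randomization makes comparable would also halve a 12-point difference to about 6, which needs roughly 87 to 92 per group. Applied to the planned change comparison, 0.3 gives about half the claimed success rate its complement: 47% to 49% power at 23.

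A second reply is that the 50% to 85% range only reflects the choice of r between 0.3 and 0.7. That is fair. At SD 17.84 and 25 per group, r = 0.8 would give about 96%. The range illustrates how much depends on r and does not bound the true power.

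Third, the printed mean may be right and one of the four SDs mistyped. The cited study is not available here, so this cannot be excluded; the effect is small either way.

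Finally, DHI is secondary and nothing in the conduct of the trial turns on this. That limits the weight of the point but does not remove it, because the plan makes an explicit 80% claim for this outcome.

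**Conclusion.** The concern holds. From the stated DHI inputs, two-sided, the requirement is 34 to 36 per group and not 23. For the planned comparison of changes, the 80% claim is true only if the DHI correlation is about 0.66 to 0.68 at 23 per group, or about 0.64 to 0.65 at 25 (0.68 for Mann-Whitney), and the plan offers no value. The arithmetic slip in the mean SD is real but minor. The conclusion rests on two-sided testing, equal SDs in both groups and at both visits, and normally distributed changes; all values of r are assumptions. The handgrip calculation and the number randomized are not called into question. This should be fixed, but it does not threaten the primary analysis.

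**What to change.** In the Sample size section:

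1. Check the four SDs against the cited study and, if they are right as printed, correct their mean to 17.84.
2. Name the formula that produced 23, its sidedness, and the baseline to follow-up correlation of DHI that it assumes, with support for that value.
3. Restate DHI power at 25 per group for the planned comparison of changes. If no correlation can be supported, give a range for 12 points: about 50% at 0.3, 64% at 0.5 and 85% at 0.7 (t-based; about 2 to 3 points lower by Mann-Whitney). Add that at 0.5, 80% power is for about 14.4 points.

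The cost is wording only, with no more patients and no change to the analysis. The stated DHI power will be less favourable unless a correlation of about 0.65 or more (0.68 for Mann-Whitney) can be supported.
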